12.4. Safety

Template Table 32 Compliance in completing solicited adverse events information (Exposed Set)

DOSE	<Each group>		
	N	n	Compliance (%)
Vaccination at Visit 1	xxx	xxx	xx.X
Vaccination at Visit 4	xxx	xxx	xx.X
TOTAL	xxx	xxx	xx.X

Short group label = long group label

N=Number of administered vaccinations

n = number of vaccinations with solicited symptom information completed

Compliance (%) = (n / N) X 100

CONFIDENTIAL

208851 (RSV OA=ADJ-002)
 Statistical Analysis Plan Amendment 2

Template Table 33 Incidence and nature of <grade 3> symptoms (solicited and unsolicited) <with causal relationship to vaccination> reported during the XX-day (Days 1-XX) post-vaccination period following each dose and overall <analysis set name>

		<Each group>					<Each group>				
					95% CI					95% CI	
Dose	Symptoms	N	n	%	LL	UL	N	n	%	LL	UL
DOSE 1	Any symptom	xxx	xxx	xx.x	xx.x	xx.x	xxx	xxx	xx.x	xx.x	xx.x
	General symptoms	xxx	xxx	xx.x	xx.x	xx.x	xxx	xxx	xx.x	xx.x	xx.x
	Local symptoms	xxx	xxx	xx.x	xx.x	xx.x	xxx	xxx	xx.x	xx.x	xx.x
DOSE 2	Any symptom	xxx	xxx	xx.x	xx.x	xx.x	xxx	xxx	xx.x	xx.x	xx.x
	General symptoms	xxx	xxx	xx.x	xx.x	xx.x	xxx	xxx	xx.x	xx.x	xx.x
	Local symptoms	xxx	xxx	xx.x	xx.x	xx.x	xxx	xxx	xx.x	xx.x	xx.x
OVERALL/DOSE	Any symptom	xxx	xxx	xx.x	xx.x	xx.x	xxx	xxx	xx.x	xx.x	xx.x
	General symptoms	xxx	xxx	xx.x	xx.x	xx.x	xxx	xxx	xx.x	xx.x	xx.x
	Local symptoms	xxx	xxx	xx.x	xx.x	xx.x	xxx	xxx	xx.x	xx.x	xx.x
OVERALL/SUBJECT	Any symptom	xxx	xxx	xx.x	xx.x	xx.x	xxx	xxx	xx.x	xx.x	xx.x
	General symptoms	xxx	xxx	xx.x	xx.x	xx.x	xxx	xxx	xx.x	xx.x	xx.x
	Local symptoms	xxx	xxx	xx.x	xx.x	xx.x	xxx	xxx	xx.x	xx.x	xx.x

Short group label = long group label

For each dose:

N = number of subjects with the corresponding administered dose

n/% = number/percentage of subjects presenting at least one type of symptom following the corresponding dose

For overall/dose:

N = number of administered dose

n/% = number/percentage of doses followed by at least one type of symptom

For overall/subject:

N = number of subjects with at least one administered dose

n/% = number/percentage of subjects presenting at least one type of symptom

95% CI = Exact 95% confidence interval; LL = lower limit, UL = upper limit

CONFIDENTIAL208851 (RSV OA=ADJ-002)
Statistical Analysis Plan Amendment 2**Template Table 34 Incidence of any symptoms (solicited and unsolicited) resulting in medically attended visit, reported during the 30-day (Days 1-30) post-vaccination period following each dose and overall <analysis set name>**

Dose	Symptoms	<Each group>						<Each group>					
					95% CI					95% CI			
		N	n	%	LL	UL	N	n	%	LL	UL		
DOSE 1	Any symptom	xxx	xxx	xx.x	xx.x	xx.x	xxx	xxx	xx.x	xx.x	xx.x		
DOSE 2	Any symptom	xxx	xxx	xx.x	xx.x	xx.x	xxx	xxx	xx.x	xx.x	xx.x		
OVERALL/DOSE	Any symptom	xxx	xxx	xx.x	xx.x	xx.x	xxx	xxx	xx.x	xx.x	xx.x		
OVERALL/SUBJECT	Any symptom	xxx	xxx	xx.x	xx.x	xx.x	xxx	xxx	xx.x	xx.x	xx.x		

Short group label = long group label

For each dose:

N = number of subjects with the corresponding administered dose

n/% = number/percentage of subjects presenting at least one type of symptom following the corresponding dose

For overall/dose:

N = number of administered dose

n/% = number/percentage of doses followed by at least one type of symptom

For overall/subject:

N = number of subjects with at least one administered dose

n/% = number/percentage of subjects presenting at least one type of symptom

95% CI = Exact 95% confidence interval; LL = lower limit, UL = upper limit

Template Table 35 Incidence of solicited local symptoms reported during the 7-day (Days 1-7) post-vaccination period following each dose and overall <analysis set name>

Dose	Symptom	Type	<Each group>					
						95 % CI		
			N	n	%	LL	UL	
DOSE 1	<Each symptom>	All						
		Grade ≥2						
		Grade 3						
DOSE 2	<Each symptom>	All						
		Grade ≥2						
		Grade 3						
OVERALL/DOSE	<Each symptom>	All						
		Grade ≥2						
		Grade 3						
OVERALL/SUBJECT	<Each symptom>	All						
		Grade ≥2						
		Grade 3						

Short group label = long group label

For each dose:

N = number of subjects with the corresponding documented dose

n/% = number/percentage of subjects reporting the type of symptom at least once following the corresponding dose

For Overall/dose:

N = number of documented doses

n/% = number/percentage of doses followed by at least one type of symptom

For Overall/subject:

N = number of subjects with at least one documented dose

n/% = number/percentage of subjects reporting the type of symptom at least once

95%CI = Exact 95% confidence interval; LL = lower limit, UL = upper limit

CONFIDENTIAL208851 (RSV OA=ADJ-002)
Statistical Analysis Plan Amendment 2**Template Table 36 Incidence of solicited general symptoms reported during the 7-day (Days 1-7) post-vaccination period following each dose and overall <cohort name>**

Dose	Symptom	Type	<Each group>			
			95 % CI			
			N	n	%	LL
DOSE 1	<Each symptom – except fever>	All				
		Grade ≥2				
		Grade 3				
		Related				
		Grade ≥2 Related				
		Grade 3 Related				
	Fever (°C)	All				
		≥38.0				
		>38.5				
		>39.0				
		>39.5				
		>40.0				
		Related				
		≥38.0 Related				
		>38.5 Related				
	DOSE 2	All				
		Grade ≥2				
		Grade 3				
		Related				
		Grade ≥2 Related				
		Grade 3 Related				
		All				
		≥38.0				
		>38.5				
		>39.0				
		>39.5				
		>40.0				
		Related				
		≥38.0 Related				
	OVERALL/DOSE	All				
		Grade ≥2				
		Grade 3				
		Related				
		Grade ≥2 Related				
		Grade 3 Related				
		All				
		≥38.0				
		>38.5				
		>39.0				

CONFIDENTIAL

208851 (RSV OA=ADJ-002)
 Statistical Analysis Plan Amendment 2

Dose	Symptom	Type	<Each group>		
			N	n	%
			95 % CI	LL	UL
		>39.5			
		>40.0			
		Related			
		≥38.0 Related			
		>38.5 Related			
		>39.0 Related			
		>39.5 Related			
		>40.0 Related			
OVERALL/SUBJECT	<Each symptom – except fever>	All			
		Grade ≥2			
		Grade 3			
		Related			
		Grade ≥2 Related			
		Grade 3 Related			
	Fever (°C)	All			
		≥38.0			
		>38.5			
		>39.0			
		>39.5			
		>40.0			
		Related			
		≥38.0 Related			
		>38.5 Related			
		>39.0 Related			
		>39.5 Related			
		>40.0 Related			

Short group label = long group label

For each dose:

N = number of subjects with the corresponding documented dose

n/% = number/percentage of subjects reporting the type of symptom at least once following the corresponding dose

For Overall/dose:

N = number of documented doses

n/% = number/percentage of doses followed by at least one type of symptom

For Overall/subject:

N = number of subjects with at least one documented dose

n/% = number/percentage of subjects reporting the type of symptom at least once

95%CI = Exact 95% confidence interval; LL = lower limit, UL = upper limit

CONFIDENTIAL208851 (RSV OA=ADJ-002)
Statistical Analysis Plan Amendment 2**Template Table 37 Number of days with </local/general> solicited symptoms during <the 7-day (Days 1-7), the whole> post-vaccination period <analysis set name>**

[figure not shown]
		<Each group>	
Dose	Symptom	Statistic	Value
DOSE 1	<Each symptom>	n	
		Mean	
		Minimum	
		Q1	
		Median	
		Q3	
		Maximum	
DOSE 2	<Each symptom>	n	
		Mean	
		Minimum	
		Q1	
		Median	
		Q3	
		Maximum	
OVERALL/DOSE	<Each symptom>	n	
		Mean	
		Minimum	
		Q1	
		Median	
		Q3	
		Maximum	

Short group label = long group label

n = number of doses with the symptom

Q1 = 25th percentile

Q3= 75th percentile

CONFIDENTIAL208851 (RSV OA=ADJ-002)
Statistical Analysis Plan Amendment 2**Template Figure 9 Incidence of solicited <local, general> adverse events reported during the 7-day (Days 1-7) post-vaccination period following each dose <Exposed set>**

Short group label = long group label

Note: this graph is provided as an example. It will be adapted to display the percentage of subjects reporting each local or general symptom, any grade and grade 3, by group and by dose. Template will be discussed at the time of the dry-run.

CONFIDENTIAL208851 (RSV OA=ADJ-002)
Statistical Analysis Plan Amendment 2**Template Table 38 Percentage of subjects reporting the occurrence of <grade 3> unsolicited AEs classified by MedDRA Primary System Organ Class and Preferred Term <with causal relationship to vaccination> within the 30-day (Days 1-30) post-vaccination period <analysis set name>**

				<Each group> N=XXXX					Total N=XXXX				
				95% CI					95% CI				
Primary System Organ Class (CODE)	Preferred Term (CODE)	n*	n	%	LL	UL	n*	N	%	LL	UL		
At least one symptom		xxx	xxx	xx.x	xx.x	xx.x	xxx	Xxx	xx.x	xx.x	xx.x		
<each SOC (SOC code)>		xxx	xxx	xx.x	xx.x	xx.x	xxx	Xxx	xx.x	xx.x	xx.x		
... <each PT (PT code)>		xxx	xxx	xx.x	xx.x	xx.x	xxx	Xxx	xx.x	xx.x	xx.x		
...													

Short group label = long group label

At least one symptom = at least one symptom experienced (regardless of the MedDRA Preferred Term)

N = number of subjects included in the considered analysis set in each group

n* = number of events reported

n/% = number/percentage of subjects reporting the symptom at least once

95% CI = exact 95% confidence interval; LL = Lower Limit, UL = Upper Limit

Template Table 39 List of (S)AEs and solicited adverse events leading to study/treatment discontinuation <Exposed set>

Group	Sub. No	Country	Gender	Race	AE Description	Preferred Term	SAE	Causality	Outcome	Vaccination and visit	Type of discontinuation *

Short group label = long group label

* type of discontinuation refers to whether the discontinuation is a treatment discontinuation or study follow-up discontinuation

Template Table 40 Listing of potential immune-mediated disorders (pIMDs) reported as identified by predefined list of preferred terms and/or by investigator assessment <analysis set name>

Group	Sub. Group	Gender	Country	Race	Age at onset (Year)	Verbatim	Preferred Term	Primary System Organ Class
<each group>								

Group	Sub. Group	Medical visit type	Dose	Day of onset	Duration	Intensity	Causality	Outcome	SAE (Y/N)	pIMD source
<each group>										

Short group label = long group label

CONFIDENTIAL208851 (RSV OA=ADJ-002)
Statistical Analysis Plan Amendment 2**Template Table 41 Listing of SAEs <analysis set name>**

Group	Sub. No.	Gender	Country	Race	Age at onset (Year)	Verbatim	Preferred Term
<each group>							

Group	Sub. No.	Primary System Organ Class	Medical visit type	Dose	Day of onset	Duration	Intensity	Causality	Outcome
<each group>									

Short group label = long group label

Template Table 42 Listing of pregnancies reported during the study period in Part A <analysis set name>

Group	Sub. No.	Count	Race	Age at vaccination	Previous Dose	LM P date	Days between LMP-vacc	Age at delivery (Year)	Date of delivery	Pregnancy Outcome	Date of outcome	Gestational weeks at birth/miscarriage/termination

Short group label = long group label

LMP=Last Menstrual Period

CONFIDENTIAL208851 (RSV OA=ADJ-002)
Statistical Analysis Plan Amendment 2**Template Table 43 Number and percentage of subjects taking concomitant medication during the <XX>-day (Days 1-<XX>) post-vaccination period by dose and overall <analysis set name>**

Dose		<Each group>					<Each group>				
		<95>% CI			<95>% CI		<95>% CI			<95>% CI	
		N	n	%	LL	UL	N	N	%	LL	UL
DOSE x	Any	xx	xx	xx.x	xx.x	xx.x	xx	Xx	xx.x	xx.x	xx.x
	Antipyretics										
	Prophylactic antipyretics	xx	xx	xx.x	xx.x	xx.x	xx	Xx	xx.x	xx.x	xx.x
OVERALL/DOSE	Any	xx	xx	xx.x	xx.x	xx.x	xx	Xx	xx.x	xx.x	xx.x
	Antipyretics										
	Prophylactic antipyretics	xx	xx	xx.x	xx.x	xx.x	xx	Xx	xx.x	xx.x	xx.x
OVERALL/SUBJECT	Any	xx	xx	xx.x	xx.x	xx.x	xx	Xx	xx.x	xx.x	xx.x
	Antipyretics										
	Prophylactic antipyretics	xx	xx	xx.x	xx.x	xx.x	xx	Xx	xx.x	xx.x	xx.x

Short group label = long group label

For each dose:

N = total number of subjects with the corresponding administered dose

n/% = number/percentage of subjects who took the specified type of concomitant medication at least once during the considered period

For overall/dose:

N = number of administered doses

n/% = number/percentage of doses after which the specified type of concomitant medication was taken at least once during the considered period

For overall/subject:

N = total number of subjects with at least one administered dose

n/% = number/percentage of subjects who took the specified type of concomitant medication at least once during the considered period

95% CI = Exact 95% confidence interval; LL = lower limit, UL = upper limit

CONFIDENTIAL

208851 (RSV OA=ADJ-002)
Statistical Analysis Plan Amendment 2**Template Table 44 Distribution of change from baseline in hematology and biochemistry with respect to normal laboratory ranges, 7 days post dose <1, 2> <analysis set name>**

Laboratory parameter	Range indicator at Baseline (PRE)	Range indicator at post-vaccination	<Each group>			<Each group>		
			N	n	%	N	n	%
<Each parameter>	UNKNOWN	UNKNOWN						
		BELOW						
		WITHIN						
		ABOVE						
	BELOW	UNKNOWN						
		BELOW						
		WITHIN						
		ABOVE						
	WITHIN	UNKNOWN						
		BELOW						
		WITHIN						
		ABOVE						
	ABOVE	UNKNOWN						
		BELOW						
		WITHIN						
		ABOVE						

Short group label = long group label

N = number of subjects with available results for the specified laboratory parameter and timing in a given baseline category

n/% = number/percentage of subjects in the specified category

Below = below the normal laboratory range defined for the specified laboratory parameter

Within = within the normal laboratory range defined for the specified laboratory parameter

Above = above the normal laboratory range defined for the specified laboratory parameter

Baseline= Pre-vaccination at <Day 1, Day 61>

Post-vaccination= Post vaccination at <Day 8, Day 68>

Template Table 45 Summary of hematology and biochemistry results by grade at 7 days post dose <1, 2> versus baseline (<Day 1, Day 61>) <analysis set name>

Laboratory parameter	Baseline	Post-vaccination	<each group >		
			N	n	%
<Each parameter>	Unknown	Unknown			
		<Each grade>			
	<Each grade>	Unknown			
		<Each grade>			
	Total	Unknown			
		<Each grade>			

Short group label = long group label

N = number of subjects with at least one available result for the specified laboratory parameter and follow-up period

n/% = number/percentage of subjects reporting at least once the laboratory event when the maximum grading over the follow-up period is considered

Baseline= Pre-vaccination at <Day 1, Day 61>

Post-vaccination= Post vaccination at <Day 8, Day 68>

CONFIDENTIAL208851 (RSV OA=ADJ-002)
Statistical Analysis Plan Amendment 2

Note: Templates 45 and 46 will be generated post dose 1 with results at Visit 2 (Day 8) versus baseline at Day 1, and post dose 2 with results at Visit 5 (Day 68) versus baseline at Day 61.

Template Table 46 Summary of hemoglobin change from baseline at 7 days post-dose <1, 2> (Exposed set)

Laboratory parameter	<Each group>		
	N	n	%
Hemoglobin - change from baseline	UNKNOWN		
	GRADE 0		
	GRADE 1		
	GRADE 2		
	GRADE 3		

[figure not shown]
Short group label = long group label

N = number of subjects with at least one available result for the specified laboratory parameter and follow-up period

n/% = number/percentage of subjects reporting at least once the laboratory event when the maximum grading over the follow-up period is considered

Note: This table will be generated post dose 1 with results at Visit 2 (Day 8) and Day 1 as baseline, and post dose 2 with results at Visit 5 (Day 68) and Day 61 as baseline.

Template Figure 10 Boxplot of <each hematology/biochemistry parameter> (Exposed Set)

Note: This graph is given as an example. It will be adapted to display one boxplot per group and per timepoint, all timepoints available (5 TPs: Screening, Days 1, 8, 61, 68). For Part A, one graph will be generated displaying the 4 groups. For Part B, 3 graphs will be generated displaying 4 groups: 3 RSV groups (30/60/120 -Plain, - AS01E or - AS01B) and the Placebo group.

CONFIDENTIAL208851 (RSV OA=ADJ-002)
Statistical Analysis Plan Amendment 2

**Template Table 47 Solicited and unsolicited symptoms classified by MedDRA
Primary System Organ Class and Preferred Term within the 30-day (Days 1-30) post-vaccination period including number of events - SAE excluded <analysis set name>**

			<Each group> N=XXXX			<Each group> N=XXXX		
Primary System Organ Class (CODE)		Preferred Term (CODE)	n*	n	%	n*	n	%
		At least one symptom	XXX	XXX	XX.X	XXX	XXX	XX.X
<each SOC (SOC code)>		At least one PT related to the corresponding SOC <each PT (PT code)>	XXX	XXX	XX.X	XXX	XXX	XX.X
		...	XXX	XXX	XX.X	XXX	XXX	XX.X

Short group label = long group label

At least one symptom = at least one symptom experienced (regardless of the MedDRA Preferred Term)

N = number of subjects included in the considered analysis set in each group

n* = number of events reported

n/% = number/percentage of subjects reporting the symptom at least once

**Template Table 48 Number (%) of subjects with serious adverse events during the study period including number of events reported
<analysis set name>**

			<Each group> N=XXXX			<Each group> N=XXXX		
Type of Event	Primary System Organ Class (CODE)	Preferred Term (CODE)	n*	n	%	n*	n	%
SAE		At least one symptom	XXX	XXX	XX.X	XXX	XXX	XX.X
	<each SOC (SOC code)>	<each PT (PT code)>	XXX	XXX	XX.X	XXX	XXX	XX.X
			XXX	XXX	XX.X	XXX	XXX	XX.X
Related SAE		At least one symptom	XXX	XXX	XX.X	XXX	XXX	XX.X
	<each SOC (SOC code)>	<each PT (PT code)>	XXX	XXX	XX.X	XXX	XXX	XX.X
			XXX	XXX	XX.X	XXX	XXX	XX.X
Fatal SAE		At least one symptom	XXX	XXX	XX.X	XXX	XXX	XX.X
	<each SOC (SOC code)>	<each PT (PT code)>	XXX	XXX	XX.X	XXX	XXX	XX.X
			XXX	XXX	XX.X	XXX	XXX	XX.X
Related Fatal SAE		At least one symptom	XXX	XXX	XX.X	XXX	XXX	XX.X
	<each SOC (SOC code)>	<each PT (PT code)>	XXX	XXX	XX.X	XXX	XXX	XX.X
			XXX	XXX	XX.X	XXX	XXX	XX.X

Short group label = long group label

N = number of subjects with administered dose

n/% = number/percentage of subjects reporting the symptom at least once

n* = Number of events reported

Related = assessed by the investigator as related

CONFIDENTIAL208851 (RSV OA=ADJ-002)
Statistical Analysis Plan Amendment 2**12.5. Analysis of RTI****Template Table 49 Number and percentages of subjects with at least one RSV-confirmed RTI episode post-vaccination, as measured by qRT-PCR in nasal/throat swab samples collected at assessment visit <analysis set name>**

Samples	RSV status	<Each group>				Total			
				95% CI				95% CI	
		N	n	%	LL	UL	N	n	%
Nasal/throat swab at assessment visit	RSV+								
	RSV-								
	All								

Short group label = long group label

RSV+= subjects tested RSV positive by qRT-PCR at least once

RSV-= subjects tested as RSV negative by qRT-PCR

All= subjects with at least one qRT-PCR result available

N = number of subjects in each group or in Total

n/%= number/percentage of subjects in each category

95%CI= Exact 95% confidence interval; LL = lower limit, UL = upper limit

Template Table 50 Number and percentages of subjects with at least one RSV-confirmed RTI episode post-vaccination, as measured by qRT-PCR in nasal swab samples collected at home <analysis set name>

Samples	RSV status	<Each group>				Total			
				95% CI				95% CI	
		N	n	%	LL	UL	N	n	%
Nasal swab at home	RSV+								
	RSV-								
	All								

Short group label = long group label

RSV+= subjects tested RSV positive by qRT-PCR at least once

RSV-= subjects tested as RSV negative by qRT-PCR

All= subjects with at least one qRT-PCR result available

N = number of subjects in each group

n/%= number/percentage of subjects in each category

95%CI= Exact 95% confidence interval; LL = lower limit, UL = upper limit

CONFIDENTIAL

208851 (RSV OA=ADJ-002)
 Statistical Analysis Plan Amendment 2

Template Table 51 Mean of the viral load of the RSV-confirmed RTI episodes, as measured by qRT-PCR on nasal/throat swabs, by collection time and collection method <Exposed set>

Days after RTI onset	Swab	RSV A +				RSV B +			
		N	n	%	mean	N	n	%	mean
0-2	Nasal swab at home								
	Nasal/throat swab at assessment visit								
3-4	Nasal swab at home								
	Nasal/throat swab at assessment visit								
>4	Nasal swab at home								
	Nasal/throat swab at assessment visit								

Days after RTI onset = number of days between start of RTI symptoms and collection date

N=Number of swabs with qRT-PCR results available

n/%= number/percentage of swabs tested as RSV A/B positive by qRT-PCR

mean= mean of the viral load computed on RSV A/B positive swabs

Template Table 52 Descriptive statistics of the viral load of the RSV- confirmed RTI episodes, as measured by qRT-PCR in nasal/throat swab samples collected at assessment visit <at home> <Exposed Set>

		<Each group> N=	Total N=
Type	Parameters	Value	Value
RSV A +	n		
	Mean		
	Min		
	Q1		
	Median		
	Q3		
	Max		
RSV B +	...		
All RSV +			

Short group label = long group label

RSV A+= RSV A positive samples by qRT-PCR

RSV B+= RSV B positive samples by qRT-PCR

All RSV += All RSV positive samples by qRT-PCR

N = Number of swabs with qRT-PCR results available

n= number/percentage of samples in each category

Q1 and Q3 = 25th and 75th percentiles

Min/Max = Minimum/Maximum

CONFIDENTIAL

208851 (RSV OA=ADJ-002)
 Statistical Analysis Plan Amendment 2

Template Table 53 Number and percentage of subjects reporting co-infections with respiratory viruses, as measured by multiplex PCR on RSV A/B positive RTI samples collected <at assessment visit, at home> <Exposed Set>

Categories	RSV RTI N =			
	n	%	95% CI	
			LL	UL
Influenza A Virus				
Influenza B Virus				
...				
<each virus>				
...				
Total				

N = number of swabs tested RSV positive by qRT-PCR

n/% = number/percentage of swabs tested positive by multiplex in a given category

Total= number of swabs tested positive for at least one virus

LL, UL= Exact 95% Lower and Upper confidence limits

Template Table 54 Clinical signs and symptoms associated with RTI episodes (Exposed set)

Characteristics	Categories	RSV RTI N=XXXX		Non RSV RTI N=XXXX		Total N=XXXX	
		n	%	n	%	n	%
Heart Rate increase (beats/min)	10-20						
	20-30						
	30-40						
	40-50						
	...						
Respiratory rate increase (breaths/min)	5-10						
	10-15						
	15-20						
	20-25						
	...						
Systolic blood pressure increase (mmHg)	10-20						
	20-30						
	30-40						
	40-50						
	...						
Diastolic blood pressure increase (mmHg)	10-20						
	20-30						
	30-40						
	40-50						
	...						
Oxygen saturation decrease (%)	1-2						
	3-4						
	5-6						
	7-8						

CONFIDENTIAL208851 (RSV OA=ADJ-002)
Statistical Analysis Plan Amendment 2

		RSV RTI N=XXXX	Non RSV RTI N=XXXX	Total N=XXXX			
Characteristics	Categories	n	%	n	%	n	%
	...						
Upper respiratory symptoms	<Each symptom>						
Lower respiratory symptoms	<Each symptom>						
qPCR result	RSV A+						
	RSV B+						
	RSV -						
Self-collected Nasal swab	RSV+						
	RSV-						
	NA						
Medically attended visit	Emergency room						
	Hospitalisation						
	Medical personnel						
	None						
SAE associated to the episode	Yes						
	No						

RSV RTI= RTI episode tested as RSV positive by qRT-PCR on nasal/throat swab collected at assessment visit

Non-RSV RTI= RTI episode tested as RSV negative by qRT-PCR on nasal/throat swab collected at assessment visit

N = number of RTI episodes in each category or in total

n = number of RTI episodes in the corresponding category

% = n / N x 100

For vital signs, change from baseline (increase/decrease) will be displayed by category: category of 10 units increase for heart rate, systolic and diastolic BP, 5 units increase for respiratory rate, and 1% decrease for oxygen saturation (to be adapted at the time of dry run if needed)

Template Table 55 Listing of RTI episodes reported during RTI surveillance in Part B (Exposed set)

[figure not shown]
Group	Sub. b. No.	Age at Dose 1	Sex	Episode nb	Start date of episode	End date of episode	Date of assessm ent visit	Nb of signs and sympto ms	Date nas al swa b on site	RSV A positi ve (site)	RSV B positi ve (site)	Date nas al swa b at hom e	RSV- A positi ve (hom e)	RSV- B positi ve (hom e)	Medica lly attende d visit	SAE relate d to RTI episo de
										Yes/N o	Yes/N o		Yes/N o	Yes/N o		Yes/N o

Short group label = long group label

CONFIDENTIAL

208851 (RSV OA=ADJ-002)
Statistical Analysis Plan Amendment 2

Template Figure 11 GMTs and 95% CIs of RSV A Neutralizing antibody titer at baseline for subjects reporting RTI episodes (RSV RTI vs or non RSV RTI vs No RTI), by groups pooled according to the adjuvant content <Exposed Set>

This graph is provided as an example, template will be finalized at the time of the dry-run. It will display the GMTs and 95% CIs for subjects reporting confirmed RSV RTI episodes vs subjects reporting Non-RSV RTI episodes vs subjects who did not report any RTI episode (NON RTI), in the RSV groups pooled according to the adjuvant content (Plain, AS01E, AS01B).

CONFIDENTIAL208851 (RSV OA=ADJ-002)
Statistical Analysis Plan Amendment 2**12.6. Additional templates (Amendment 1)****Template Table 56 Distribution of hematology and biochemistry parameters at baseline with respect to normal laboratory ranges <analysis set name>**

Laboratory parameter	Range indicator at baseline	<Each group>			<Each group>		
		N	n	%	N	n	%
<Each parameter>	UNKNOWN						
	BELOW						
	WITHIN						
	ABOVE						

Short group label = long group label

N = number of subjects with available results for the specified laboratory parameter in a given baseline category

n/% = number/percentage of subjects in the specified category

Below = below the normal laboratory range defined for the specified laboratory parameter

Within = within the normal laboratory range defined for the specified laboratory parameter

Above = above the normal laboratory range defined for the specified laboratory parameter

Template Table 57 Summary of follow-up time (in days) up to <DLP or last contact> (Exposed Set)

	<Each group> N=XXXX	Total N=XXXX
	Value	Value
Number of days in the study		
N	XXX	XXX
Mean	XXX.X	XXX.X
Median	XXX.X	XXX.X
Minimum	XXX	XXX
Maximum	XXX	XXX

Short group label = long group label

N = total number of subjects

Value = value of the considered parameter

N with data = number of subjects with documentation of the corresponding data

CONFIDENTIAL

208851 (RSV OA=ADJ-002)
 Statistical Analysis Plan Amendment 2

Template Table 58 Summary of subjects by unsolicited adverse event category

		<each group> N=XXXX
At least one unsolicited adverse event within 30-day of any vaccination	n* n % 95% CI	xxx xxx xx.x (xx.x ; xx.x)
At least one related unsolicited adverse event within 30-day of any vaccination	n* n % 95% CI	xxx xxx xx.x (xx.x ; xx.x)
At least one medically attended unsolicited adverse event within 30-day of any vaccination	n* n % 95% CI	xxx xxx xx.x (xx.x ; xx.x)

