- **Control:** placebo.
- **Vaccination schedule:** Two vaccine doses administered intramuscularly at Day 1 and Day 61.
- **Blinding:** observer-blind.

The vaccination phases of each study part (Epoch 002) will be observer-blind. A first statistical analysis will be performed on data available up to one month post-Dose 2 (Visit 6, Day 91). Given that summary safety results may unblind some specific subjects, the persistence phase of Part B (Epoch 003) will be considered as single-blind with subjects remaining blinded up to study end (Visit 8 [Month 14]). The investigators will not be provided with the individual data listings or with the randomization listings until the end of study analysis.

- **RTI surveillance in Part B:** Active and passive surveillance will only be carried out during RSV seasons (approximately from October to March) throughout the entire Part B of the study:
 - **Active surveillance:** study participants will be contacted by the investigator/study staff every 2 weeks to identify if they experience an RTI.
 - **Passive surveillance:** study participants are instructed to contact the investigator/study staff as soon as they experience an RTI.

At the beginning of RSV seasons, study participants will be reminded of the start of the RTI surveillance.

- **Sampling schedule:**

In Part A:

- At Screening (Pre-Day 1), a blood sample for eligibility assessment will be drawn from all subjects. In case Visit 1 occurs more than 30 days after the Screening visit, a re-screening visit should be scheduled before Visit 1 during which blood sample collection must be repeated (maximum one re-screening per subject is allowed). Medical history, physical examination and review of inclusion/exclusion criteria must be repeated if a re-screening visit occurs. Only data from the re-screening visit, if it occurs, will be taken into consideration and recorded in the electronic Case Report Form (eCRF). The subject can however only be randomized once the investigator receives the safety assessment results and confirms the eligibility criteria.
- At Day 1 (Visit 1), a blood sample for cytomegalovirus (CMV) status determination will be drawn from all subjects.
- **Blood samples for safety assessment** (hematology/biochemistry) will be drawn from all subjects on Days 1, 8, 61 and 68 (Visits 1, 2, 4 and 5).

CONFIDENTIAL

208851 (RSV OA=ADJ-002)
 Statistical Analysis Plan Amendment 2

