10.1.5. Statistical methodology**10.1.5.1. Exact confidence intervals around proportions**

The exact confidence intervals around within-group proportions are derived using the method of Clopper and Pearson [[Clopper](#), 1934].

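### The OVERALL/DOSE rows in Template Tables 33–36 and 43 put an exact binomial CI on doses as if independent, so with positive within-subject correlation that row's interval is too narrow

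*SAP*

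**What the plan says.** The design gives each subject two doses: "Two vaccine doses administered intramuscularly at Day 1 and Day 61" (SAP section 2).

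Section 12.4 fixes the OVERALL/DOSE row as follows.

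- Template Tables 33 and 34: denominator "N = number of administered dose", numerator "n/% = number/percentage of doses followed by at least one type of symptom".
- Template Tables 35 and 36: the same numerator, with denominator "N = number of documented doses".
- Template Table 43 (concomitant medication): denominator "N = number of administered doses", numerator "n/% = number/percentage of doses after which the specified type of concomitant medication was taken at least once during the considered period".

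Each table has one interval footnote covering all its rows; in Template Table 33 it reads "95% CI = Exact 95% confidence interval; LL = lower limit, UL = upper limit". Section 10.1.5.1 says what exact means: "The exact confidence intervals around within-group proportions are derived using the method of Clopper and Pearson". Neither place makes an exception for rows that count doses, and the safety sections contain no clustering adjustment.

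The analysis text is narrower than the templates. Section 5.4.1 asks for the percentage of subjects with an event, with an exact CI, after each dose and overall. The dose-level percentage with a CI appears only in the mock tables.

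**The concern.** Clopper-Pearson treats the denominator as that many independent yes/no results. In the OVERALL/DOSE row, two results usually come from the same person. If someone who reacts after Dose 1 is more likely to react after Dose 2, the row holds less information than its denominator suggests, and the printed interval is shorter than the data support.

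No safety tests are planned, so the confidence intervals are the only statement of uncertainty on reactogenicity. Section 6 sets out to characterise differences between groups, and the Day 91 analysis goes to a study report and public posting (section 7.1). An interval labelled exact 95% that in fact covers about 90% would mislead a reader who relies on that row.

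The SAP deals with the same pairing elsewhere. The Day 31/Day 91 immunogenicity model in section 5.3.2.3 has a repeated-visit covariance within subject.

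**Working it through.** The SAP states no interval width or precision for these rows, so there is no plan figure to reproduce.

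**Inputs from the SAP (section 2).** Two doses per subject. Part B has about 70 + 30 = 100 subjects per group, so 200 doses. Part A has about 12 per group, so 24 doses. An adjuvant pool of three Part B groups has about 300 subjects and 600 doses.

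**Assumptions.** The within-subject correlation rho is not in the SAP and is shown as a range. Incidence p is taken as equal after both doses, and every subject is taken to contribute two doses.

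**Step 1: variance.** With two doses per subject, P(event after both) = p² + rho·p(1−p), and the variance of the dose-level proportion over S subjects is p(1−p)(1+rho)/(2S). Independence drops the factor 1+rho. At p = 0.3, rho = 0.5, S = 100:

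- SE assumed: √(0.21/200) = 0.0324
- SE actual: √(0.21 × 1.5/200) = 0.0397
- ratio: √1.5 = 1.22

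**Step 2: exact coverage.** One subject gives 0, 1 or 2 events. At p = 0.3, rho = 0.5 the probabilities are 0.595, 0.210 and 0.195. Convolving this distribution over S subjects gives the distribution of the total. Coverage is the probability that the Clopper-Pearson interval on 2S doses contains p.

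| Setting | rho 0 | 0.1 | 0.2 | 0.3 | 0.5 | 0.7 |
|---|---|---|---|---|---|---|
| Part B group, p = 30% | 95.5 | 94.4 | 93.3 | 92.1 | 89.8 | 87.5 |
| Part B group, p = 10% | 96.7 | 95.8 | 94.8 | 93.8 | 91.8 | 89.7 |
| Part B group, p = 5% | 96.7 | 95.8 | 94.9 | 94.0 | 92.0 | 90.0 |
| Part B group, p = 2% | 96.2 | 95.3 | 94.2 | 93.1 | 90.5 | 87.2 |
| Part B group, p = 1% | 98.4 | 97.9 | 97.4 | 96.9 | 96.0 | 95.1 |
| Part A group, p = 30% | 97.7 | 96.9 | 96.1 | 95.2 | 93.3 | 91.2 |
| Pooled adjuvant group, p = 30% | 95.5 | 94.4 | 93.3 | 92.1 | 89.8 | 87.6 |

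The values are percentages. In Part A at 2%, 5% and 10% incidence, coverage is about 97% or more for rho up to 0.7.

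**Step 3: width.** For 60/200 = 30% the planned interval is 23.7% to 36.9%, 13.1 points wide. Using an effective number of doses 200/(1+rho) only as a yardstick:

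- rho 0.3: effective n 154, width 15.0 (×1.14)
- rho 0.5: effective n 133, width 16.2 (×1.23)
- rho 0.7: effective n 118, width 17.2 (×1.31)

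For 180/600 in a pooled group the planned width is 7.5 points. At rho 0.5 (effective n 400) it would be 9.2. The shortfall is about 1.7 points pooled, against about 3.0 points in a single group.

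**The case against.** Five points can be made in the plan's favour.

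- **Stated endpoints.** A reader might infer that the intervals on the primary safety endpoints are invalid. The SAP does not support that. Section 3.2.1 defines solicited and unsolicited events after each vaccination, and section 5.4.1 asks for percentages of subjects. The DOSE 1, DOSE 2 and OVERALL/SUBJECT rows supply these with each subject counted once. Template Tables 34 (medically attended events) and 43 (concomitant medication) show no listed primary endpoint. This stands.
- **Consequence.** Section 5.4.2 makes safety descriptive, and no test, threshold or decision uses the row. This stands.
- **Pooled adjuvant groups.** One might expect the pooled tables to suffer most. At 30% incidence the coverage loss is about the same as in a single group, and the shortfall in points is smaller. The larger sample does not cure the problem, but it does not worsen it either.
- **Size.** It rests on an unstated rho. The loss is small at low rho, and the conservatism of the exact method hides much of it in Part A and at 1% incidence in a single Part B group. Rarity alone is no safeguard: at 2% in Part B, coverage is 93.1% at rho 0.3. This stands in part.
- **Illustrative mocks.** Section 12 says the displays and footnotes are illustrative and will be adapted. This does not answer the point, because nothing tells the programmer to treat the dose row differently.

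**Conclusion.** The point holds for the OVERALL/DOSE row of Template Tables 33–36 and 43, and for no other row. The direction is certain for any positive rho. Negative rho would make the interval too wide, but is implausible for reactogenicity.

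At 30% incidence in a Part B group, the loss of coverage runs from about half a point below nominal at rho 0.1 to about 7.5 points at rho 0.7. These sizes assume two doses per subject and equal incidence after each dose. What results is overstated precision in a descriptive row. Correcting it is worthwhile mainly because it costs so little.

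**What to change.** Remove the CI from the OVERALL/DOSE rows of Template Tables 33–36 and 43, keeping n, N and %. Template Table 37 already shows this row without a CI. Let the per-dose and OVERALL/SUBJECT intervals carry the uncertainty.

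If a dose-level interval is wanted, use one with subject as the cluster that allows one or two doses per subject, such as GEE with a robust variance. State it in section 10.1.5.1 and in the table footnotes, with a rule for cells with few or no events. Do not use a fixed division of the dose count by 1 + rho. It presumes two doses from everyone, whereas Template Tables 11 and 16 provide for one-dose subjects, and rho cannot be estimated reliably in sparse cells or with 12 subjects.

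The first option costs a wording change and a small programming change, and the row loses its interval. The second costs more programming and gives a wider interval. Neither needs new data.
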